2.2 BACKGROUND

Preliminary Data

aiTBS acute efficacy: Numerous past reports have found iTBS of the L-DLPFC to be an effective treatment for depression^{87,164,177}. In our first open-label study of aiTBS for treatment of the most severe, treatment-resistant depression (MSM score of every patient was 14)^{181,182}, we found a 76% reduction in depression symptoms (HDRS-17) with 5/6 participants showing >50% reduction in symptoms and 4/6 remitting from depression after 5 days of aiTBS, despite having failed ECT, conventional rTMS, numerous medications (including ketamine), and psychotherapy.

We recently published our open-label follow-up study¹⁴⁹. We have treated 31 participants with highly treatment resistant depression (Maudsley Staging Method score ≥ 11) with only 1 drop-out during the 5-day treatment course. We observed an extremely high rate of remission (28/31, 90%, MADRS < 10) in less than 5 days of treatment (mean days to remission = 2.96 ± 1.48). After 5 days of aiTBS there was an 88% reduction in mean MADRS with scores from 37.71 ± 7.24 to 4.65 ± 6.46 . Notably, our results are nearly identical for the subset of 22 patients with major depressive disorder (MDD, the 9 other patients had bipolar depression or Parkinson's-related depression), as this MDD sample is more reflective of the population we plan to target in this study. Mean Hamilton Depression Rating Scale-6 (HDRS-6) scores decreased with each additional day of stimulation over the entire 5 day stimulation course. None of the participants who had previously not responded to an FDA-approved rTMS treatment course responded after the first day of aiTBS, when the equivalent amount of stimulation as an FDA-approved treatment course was administered. However, 76.92% of the rTMS non-responders in our study did respond to aiTBS, suggesting that FDA-approved protocols may be underdosing. Mean HAMD-17 significantly decreased from $26.280 (\pm 4.909, \text{range } 20-35)$ at baseline to $4.722 (\pm 4.599, \text{range } 0-16)$ after treatment ($t_{(17)} = 11.275, p < .001$). Mean MADRS significantly decreased from $33.220 (\pm 5.208, \text{range } 27-44)$ at baseline to $4.833 (\pm 5.813, \text{range } 0-19)$ after treatment ($t_{(17)} = 14.915, p < .001$). Baseline HAMD-17 and MADRS scores were highly correlated ($r = .817, p < .001$), as were the percent-change scores from baseline to post-treatment ($r = .948, p < .001$). MADRS was used as the primary clinical outcome for all fc analyses, and all results are equivalent for HAMD-17.

2.3 RISK/BENEFIT ASSESSMENT

2.3.1 KNOWN POTENTIAL RISKS

Immediate Risks:

aiTBS: Seizure risk is generally the most significant immediate concern associated with rTMS, at approximately 1:30,000 sessions for traditional high frequency rTMS¹⁸³. However, there are no reported seizures with the iTBS (excitatory) parameters that will be used in this study¹⁸⁴. Only one case of TBS has resulted in seizure, and this case was associated with the use of continuous (inhibitory) TBS at $\geq 100\%$ resting motor threshold^{184,185}, whereas we will use iTBS at 90%. Any seizure that theoretically could occur would likely be self-limited and lead to no residual neurological impairment. Seizures induced by rTMS are rare, brief and don't result in sequelae, with no events of status epilepticus ever being reported¹⁸³.

Another potential immediate risk is that of induction of mania. Although there have been no such cases of mania induced by iTBS, there have been at least 13 cases of rTMS-induced mania reported from fixed-frequency rTMS¹⁸⁶. The rTMS-induced mania rate reported by Xia et al was 0.84% as compared to 0.73% for sham, which were not significantly different from each other. Most of the reported cases of rTMS-induced mania were in individuals with bipolar disorder, a population that will not be included in the current study. Nevertheless, it is possible that patients could develop symptoms of hypomania or mania following stimulation. Patients' symptoms will be monitored carefully by both members of the research team and clinical staff. The YMRS will be administered daily to check for mania symptoms. If patients show hypomanic/manic symptoms, no further stimulation will be administered and the patient's clinician will be notified.

Another potential risk is mild pain at the site of stimulation, which occurs during stimulation only, and which wanes with each session. There is also a risk of psychological distress related to this pain, should it occur, though discomfort associated with rTMS is typically mild, and not distressing when participants are reassured it is not dangerous.

Finally, expected AEs have been reported in association with iTBS in a recent large RCT¹⁸⁷, and a full list of expected AEs can be found in Section 8.3.3.3.

MRI: There are some contraindications that may prevent a participant from having a scan; however, all participants will be screened prior to scanning to evaluate these risk factors¹⁸⁸. Due to the strength of the magnetic field, contraindications include participants with heart pacemakers, metallic foreign bodies in their eye, and brain aneurysm clips, as the magnetic field may dislodge the metal leading to injury^{184,188}. Possible side effects of undergoing an MRI are listed in 8.3.3.3.

Lidocaine: Possible side effects associated with Lidocaine are mentioned in 8.3.3.3.

Confidentiality: A risk of all clinical studies is that they collect personal information that may be seen by individuals not associated with the study. This could lead to psychological, social, cultural and legal risks. To protect participants' confidentiality, a numerical system will be used as unique identifiers, and identifying information will not be stored with the data. Electronic data will be stored on shared computer drives and in REDCap, a HIPAA compliant electronic data capture software, maintained by the university under rigorous firewall and password protection. Secured information linking participant's ID with protected health information will be separated from the unidentified data.

Long-range Risks: No long-range risks associated with iTBS or routine MRI have been reported, and none are anticipated for this study.

Alternative Treatments and Procedures: There are several other treatments for severe depression; however, none carry the optimal low risk/benefit ratio or quick action of aiTBS. The most realistic alternatives would be electroconvulsive therapy, conventional rTMS, and/or medications. Although the current FDA-approved form of conventional rTMS is effective, a typical treatment course takes 6 weeks to complete and the open label efficacy rates are lower than this approach and participation in this protocol does not preclude a subsequent traditional rTMS⁸². Similarly, an acute course of electroconvulsive therapy takes typically 1 month to complete, carries greater risks than rTMS¹⁸⁹, and cultural acceptance is low¹⁹⁰. Medications take months to begin working and their efficacy is severely limited compared to ECT or rTMS^{9,191}. Esketamine/Ketamine could also be considered given their rapid onset of action, but their effects are short-lived¹⁹².

2.3.1 KNOWN POTENTIAL BENEFITS

Based on our previous open-label studies^{172,193}, many of the research participants who receive active aiTBS are likely to achieve rapid improvements in their depression symptoms, with associated improvement in their social and occupational functioning. Identifying an efficacious treatment for a subject's depression may have long-range benefits as well, in that treatment effects may be sustained and the subject will have identified an effective potential treatment after multiple treatment failures.

Furthermore, the information gained from this study will inform further optimization and personalization of rTMS therapy for TRD. Specifically, this study will provide invaluable data on the transition from the depressed network configuration to the remission network configuration and how this transition relates to aiTBS and depression symptoms. Our results might provide a neurobiological basis for L-DLPFC inhibition of sgACC as a causative factor in the development of TRD, allowing for potentially more effective mood control.

2.3.2 ASSESSMENT OF POTENTIAL RISKS AND BENEFITS

Given the high degree of safety of MRI and rTMS¹⁸³, there is a low risk to high benefit ratio for this intervention. rTMS will be performed and monitored according to widely accepted principles that maximize safety¹⁸³. Based on our previous open-label studies^{172,193}, many of the research participants who receive active aiTBS are likely to achieve rapid improvements in their depression symptoms, with associated improvement in their social and occupational functioning.

Furthermore, the information gained from this study will inform further optimization and personalization of TMS therapy for TRD. Specifically, this study will provide invaluable data on the transition from the depressed network configuration to the remission network configuration and how this transition relates to aiTBS and depression symptoms. Our results might provide a neurobiological basis for L-DLPFC inhibition of sgACC as a causative factor in the development of TRD, allowing for potentially more effective mood control. Hence, we believe that the risks associated with this study are minimal compared to the knowledge gained.

3 OBJECTIVES AND ENDPOINTS

OBJECTIVES	ENDPOINTS	JUSTIFICATION FOR ENDPOINTS
Primary		
To establish a resting state functional connectivity (RS FC) dose-response curve of active versus sham aiTBS.	Change in RS FC between the sgACC and DMN over 5-days of active aiTBS as compared to sham aiTBS. RS FC will be measured on the morning of each intervention day and the day following intervention.	We hypothesize that participants (n=50) receiving active aiTBS applied to DLPFC-sgACC will demonstrate a significant attenuation of RS FC between sgACC and DMN compared to sham (n=50) after each day of stimulation and these effects will accumulate linearly over the course of the 5 days of aiTBS. The central, consistent change in neurocircuitry observed in depression is hyperconnectivity between the SCC and DMN ⁴³ and our preliminary data involving RS FC changes from aiTBS demonstrates highly significant changes ¹⁹⁴ .
Secondary		

(a) To determine the relationship between active versus sham aiTBS-induced clinical improvement (as measured by reduction of the MADRS-S) and changes in RS FC between the sgACC and DMN.
 
(b) To determine the relationship between acute mood state (as measured by the IMS-12) and changes in RS FC between the sgACC and DMN in those receiving active versus sham aiTBS.
	
(a) Relationship between clinical improvement (measured by the MADRS-S) and RS FC between the sgACC and DMN.
 
MADRS-S will be collected at baseline, the end of each intervention day, the day following intervention, and 1-month after intervention. RS FC will be measured on the morning of each intervention day and the day following intervention.
 
(b) Relationship between acute mood state (measured by the IMS-12) and RS FC between the sgACC and DMN.
 
IMS-12 will be collected at baseline, on the morning of each intervention day, and the day following intervention. RS FC will
	Our mechanistic hypothesis is that active versus sham aiTBS-induced improvement in mood will be linear, related to session number (accumulated pulse dose), and will be associated with (accumulated) decrease in sgACC- DMN resting state functional connectivity, as compared to sham.

	be measured on the morning of each intervention day and the day following intervention.	
Exploratory		

(a) To determine the relationship between active versus sham aiTBS-induced clinical improvement (as measured by reduction of the MADRS-S) and changes in RS FC in an unbiased, whole-brain analysis.
 
(b) To determine the relationship between acute mood state (as measured by the IMS-12) and changes in RS FC in an unbiased, whole-brain analysis in those receiving active versus sham aiTBS.
	
(a) Relationship between active versus sham aiTBS-induced clinical improvement (as measured by reduction of the MADRS-S) and changes in whole-brain RS FC.
 
MADRS-S will be collected at baseline, on each intervention day, and the day following intervention. Whole-brain RS FC will be measured on the morning of each intervention day and the day following intervention.
 
(b) Relationship between acute mood state (as measured by the IMS-12) and changes in whole-brain RS FC in those receiving active versus sham aiTBS
 
IMS-12 will be collected at baseline, on the morning each intervention day, and the day following intervention. Whole-brain RS FC will be measured on the morning of each intervention day and the day following intervention.
	
Our hypothesis is that greater network segregation will be detected for better clinical outcomes and that a combination of the functional connectivity features involving emotion regulation will have better prediction accuracy for clinical outcomes. This alternative approach will allow us to identify other RS FC changes with especially large effect sizes, which would be important candidates for further investigation in future studies.

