4 STUDY DESIGN

4.1 OVERALL DESIGN

Hypothesis: Participants (n=50) receiving active aiTBS applied to DLPFC-sgACC will demonstrate a significant attenuation of RS FC between sgACC and DMN compared to sham (n=50) after each day of stimulation and these effects will accumulate linearly over the course of the 5 days of aiTBS.

Phase: This is a mechanistic study similar to a phase 2 trial.

Trial Design: Randomized, sham-controlled, double-blinded mechanistic study.

Methods to Minimize Bias: This study will achieve robust and unbiased results via several design features including: explicit inclusion/exclusion criteria; randomization of intervention condition; the use of a validated sham control; blinding; use of validated laboratory and interview/self-report measures and methods; explicit hypotheses and corresponding planned statistical analyses; power estimates; planned handling of retention/attrition and missing data; and, careful consideration of potential confounds. All experimental details will be reported in a fully transparent manner to support replication.

Dose Escalation: TMS stimulation dose will be individually determined according to 90% rMT plus depth correction, and then the aiTBS protocol will be administered with a consistent dose across all participants receiving active stimulation of 18,000 pulses/day and 90,000 pulses/course.

The goal of treatment in this study is to ensure the correct amount of treatment (90% of motor threshold) is received in the target location (L-DLPFC) rather than under-stimulating and under- treating participants. Depth correction accounts for the variable distances between the scalp and motor hotspot and scalp and treatment target from person to person. In other words, this is a personalized treatment intensity that takes into account individual variability. However, to ensure safety we never treat higher than 120% of the person's resting motor threshold, which is the standard TMS treatment intensity in routine clinical practice.

Study Arms: Two arms, active vs sham in 50:50 randomization

Site(s): Single Site (Department of Psychiatry & Behavioral Sciences, Stanford University)

Name of Study Intervention: Accelerated intermittent theta-burst stimulation (aiTBS).

Interim Analysis: N/A

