The null hypothesis (i.e. no difference in change in FC between active and sham intervention groups) will be rejected if the intervention group x time interaction has a p-value < 0.05. Data will be presented as least-squares means with standard errors.

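### The plan hypothesises linear accumulation over five days, but no planned analysis tests it, and a significant primary result would not show that the effect keeps building through day 5

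*Combined protocol and SAP*

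**What the plan says.** - **Objective.** Sections 1.1 and 3 make an FC dose-response curve, active against sham, the primary objective.
- **Shape hypothesised.** For FC, sections 3 and 4.1 say that "these effects will accumulate linearly over the course of the 5 days of aiTBS". For mood, section 3 says that "aiTBS-induced improvement in mood will be linear, related to session number (accumulated pulse dose", and the synopsis (1.1) says much the same.
- **Formal hypotheses.** Section 9.1 does not mention linearity. It asks for a larger FC reduction on active than on sham, and for a stronger association between FC change and mood.
- **Primary test.** In 9.4.2 the mixed model has group, time and their interaction, with time as a fixed factor. The null is rejected if the "intervention group x time interaction has a p-value < 0.05". Least-squares means are presented, and post-hoc pairwise comparisons are corrected for multiplicity.
- **Mood.** Section 9.4.3 correlates the baseline-to-post change in FC with the change in MADRS-S and IMS-12 within each arm, then compares the two coefficients.
- **Pilot (2.2).** It reports an "88% reduction in mean MADRS with scores from 37.71 ± 7.24 to 4.65 ± 6.46", "mean days to remission = 2.96 ± 1.48" days, and that mean HDRS-6 "scores decreased with each additional day of stimulation over the entire 5 day stimulation course".

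**The concern.** The trial's question is how the effect grows with dose, and the stated answer is a straight line through five days. Section 4.1 lists, among its safeguards against bias, that each explicit hypothesis has a planned analysis to match. For linearity there is none. An omnibus interaction says that the arms diverge somewhere over the six scans. It does not say whether they are still diverging after day 3.

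At stake is the reading of a positive result. Reported beside the linear hypothesis, a significant interaction could be taken to show that the effect accumulates through all 90,000 pulses, including the 36,000 delivered on days 4 and 5. The test gives no support for that step. The daily mood scores, which could address shape directly, enter the confirmatory analysis only as a change between two time points.

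**Working it through.** **1. Timing of the scans.** The Visit 3 scan precedes the first session, and each later scan is taken the following morning. At 18,000 pulses a day, Visit 6 follows 3 × 18,000 = 54,000 pulses and Visit 8 follows 5 × 18,000 = 90,000. Visit 6 to Visit 8 therefore isolates the last 36,000. IMS-12 is taken on the same mornings.

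**2. The plan's sample size.** Section 9.2 uses alpha = 0.05/(10 × 4 × 2) = 0.000625, effect size 1 and power 0.80. A two-sided two-sample t-test gives 39.3, so 40 per arm, as stated. I use 40 per arm and d = 1 on the full-course change below. The correlation between scans is not in the documents and is assumed.

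**3. Can the primary test tell the shapes apart?** Two shapes for the active-minus-sham difference at Visits 3 to 8, as fractions of the full effect:
- linear: 0, 0.2, 0.4, 0.6, 0.8, 1
- complete by day 3: 0, 1/3, 2/3, 1, 1, 1

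Noncentral-F power for the interaction, 5 numerator df, 5 × (2 × 40 − 2) = 390 denominator df, AR(1) correlation 0.3 to 0.9:

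| Full-course d | Linear | Complete by day 3 |
|---|---|---|
| 1 | 0.95-0.97 | 0.99 or more |
| 0.7 | 0.66-0.72 | 0.81-0.86 |

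Significance is at least as likely under the plateau as under linearity. A linear-trend test used alone does no better: it is significant in about 99-100% of trials under either shape at d = 1.

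**4. What a late contrast can do.** Under linearity, Visit 6 to 8 carries 2/5 = 0.4 of the effect.
- Exchangeable correlation 0.5: the SD of a change is √(2 − 2 × 0.5) = 1 for any pair of visits, so late d = 0.4 and power with 40 per arm is 42%.
- AR(1) 0.5: late d = 0.4 × √(2 − 2 × 0.5⁵)/√(2 − 2 × 0.5²) = 0.4 × 1.392/1.225 = 0.455, power 52%.
- AR(1) 0.8: late d = 0.4 × 1.160/0.849 = 0.547, power about 68%.

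If the effect is flat after day 3, the contrast is significant in 5%. It separates the shapes, with moderate power.

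**5. Lack of fit (linear against categorical day).** The same noncentral-F calculation on the four contrasts orthogonal to a straight line, with 4 numerator df, gives power of 38% to 74% against the day-3 plateau over AR(1) 0.3 to 0.9. A non-significant result would not establish linearity.

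**6. What the pilot adds.** (37.71 − 4.65)/37.71 = 87.7%, which reproduces the stated 88%. A straight line between the means falls 33.06/5 = 6.61 points a day, is at 37.71 − 3 × 6.61 = 17.9 on day 3, and crosses 10 at (37.71 − 10)/6.61 = 4.19 days. The reported mean time to remission is 2.96 days. Individuals simulated as exactly linear from the pilot means and SDs first remit at mean day 4.3-4.5, so steady straight-line improvement in each patient fits poorly.

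That does not carry over to the group mean. If remissions fall evenly on days 1 to 5 (mean 3, SD √2 = 1.41, close to the reported 2.96 ± 1.48) and each is abrupt, the mean falls 20% a day. That is exactly linear, with 60% of the gain by day 3.

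**The case against.** **The shape would be visible anyway.** Time is a factor, so the model yields daily least-squares means, and a Visit 6 against Visit 8 comparison could be among the corrected post-hoc pairs. This stands in part: a plateau would not be hidden. But the plan does not name that comparison, does not say whether the pairs are within arm or active minus sham, and gives no rule for claiming accumulation. If the correction covers all 6 × 5/2 = 15 pairs of scans (my assumption), alpha becomes 0.05/15 = 0.0033 and the power of the late contrast drops from 42-68% to about 12-29%.

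**The decision rule never claims linearity.** True. Section 9.4.2 rejects only the null of no difference in FC change, and the mood analysis cannot credit any particular day. The gap is between the hypothesis and the tests, not an error within a test. A falsifiable linear hypothesis is legitimate.

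**A stronger reading is tempting.** A reader might infer that the pilot contradicts linearity because some 85% of the mood gain came by day 3. That figure arises from placing the group mean at the remission threshold on day 2.96: (37.71 − 10)/33.06 = 84%, or 87% with a threshold of 9. The documents do not support it:
- No day-3 score is reported.
- Mean time to remission is not the day on which the mean score crosses 10. It is also defined only for the 28 remitters, while the means cover all 31.
- Trajectories with a similar time to remission give anywhere from about 60% to 87% by day 3.
- The only day-by-day statement says that mean HDRS-6 fell on each of the five days.

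The rate of 12 HDRS-17 points a day in section 2.1 does not help either. It is offered conditionally, and it sits badly with the 21.56-point fall over the whole course in 2.2. That is an inconsistency about rate and says nothing on shape.

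**Conclusion.** The point holds as a mismatch between hypothesis and analysis. Linear accumulation is stated for FC and mood, and nothing in 9.4.2 or 9.4.3 tests it. Under the assumptions above, a significant interaction is about equally likely whether the effect is linear or complete by day 3, so it cannot be cited for accumulation through 90,000 pulses. The pilot is compatible with front-loading under some trajectories and with a linear group mean under others. It leaves the question open and does not contradict the hypothesis. It also gives no daily FC data, and FC is the primary endpoint.

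The power figures rest on 40 evaluable per arm, full-course d = 1 and assumed correlations. The plateau at day 3 is a limiting case chosen for contrast, not an expected result.

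**What to change.** In 9.4.2, prespecify from the mixed model already planned:
- (a) a linear-trend group-by-time contrast, with a lack-of-fit test of linear against categorical day;
- (b) active-minus-sham contrasts for early change (Visit 3 to Visit 6) and late change (Visit 6 to Visit 8).

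Apply the same set to daily IMS-12. The primary decision rule can stay as it is.

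Report the late contrast as an estimate with its confidence interval. Claim accumulation through day 5 only if the interval excludes zero in favour of active. If it is inconclusive, claim neither accumulation nor a plateau. Treating a non-significant late contrast as a plateau would be wrong in about 58% of trials under true linearity at 42% power (1 − 0.42).

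The cost is SAP wording and a few contrasts, settled before unblinding, on data already scheduled. The downside is that, with about 40-70% power for the late contrast even under true linearity, the linear claim becomes harder to make.
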